#### 9.1.4 Secondary Objective Parameters

The secondary parameters of the study, evaluated at each study visit, are as follows:

- Surgical parameters of the AccuLIF cohort, including operative time, estimated blood loss and length of stay.
- The occurrence of neurologic complications, defined as abnormal changes from the pre-operative to post-operative neurologic evaluations.
- Changes in clinical outcomes, comparing pre- and post-operative patient measured outcomes defined as VAS, ODI and quality of life (QOL) as measured by SF-12.
- The occurrence and frequency of additional complications of the AccuLIF cohort, including infection and nonunion.
- Standard radiographic outcomes defined as; fusion status, cage placement, migration / subsidence and parameters of supplemental fixation hardware including screw placement and subsidence.

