### 2.2 Secondary

The secondary objectives of the study are:

- To observe surgical parameters of the AccuLIF cohort.  
Defined as; operative time, estimated blood loss and length of stay.
- To assess the occurrence of neurologic complications by comparing pre-operative and postoperative neurologic evaluation.
- To assess clinical outcomes by comparing pre and post-operative patient measured outcomes defined as VAS, ODI and quality of life (QOL) as measured by SF-12 of the AccuLIF cohort.

CONFIDENTIAL

This material is the property of Stryker Spine. Do not disclose or use except as authorized in writing by Stryker.  
Page 16

- To observe the occurrence and frequency of additional complications of the AccuLIF cohort, including infection and nonunion.
- To observe standard radiographic outcomes defined as; fusion status, cage placement, migration / subsidence and parameters of supplemental fixation hardware including screw placement and subsidence.

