# 6 Device Description

## 6.1 Study Device

The AccuLIF system was launched by Stryker Spine in 2014. AccuLIF is a comprehensive system of instruments and implants, including spacers comprised of titanium alloy, stainless steel and silicone rubber, with different size and height offerings. The AccuLIF expandable lumbar interbody technology offers surgeon users the ability to insert an interbody device at a smaller starting height, place the device in the desired position within the disc space, and then expand the device to the desired height based on patient anatomy to ensure endplate-to-endplate fit.

The patented expansion mechanism utilizes hydraulic pressure to expand the implant in 1mm increments to fill the disc space. The hydraulic expansion mechanism provides tactile and visual feedback during expansion and the mechanical lock offers confirmation that the implant is locked. The small starting height of the implant is designed to help preserve endplate structural integrity, minimize impaction forces during insertion, help reduce nerve root retraction on insertion and during expansion, and help to reduce the potential for neural injury during insertion of the implant. This procedure is done via a transforaminal lumbar interbody fusion, (TLIF) technique and can be performed as an open, MIS or LIS procedure. In an open or minimally invasive TLIF approach, the interbody space is generally accessed from a posterior approach, and an AccuLIF TL implant is inserted into the disc space after discectomy and endplate preparation.

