# 7 Study Evaluations

## 7.1 Pre-operative Visit

During the preoperative (first) visit, inclusion/exclusion criteria will be assessed. After eligibility has been confirmed by the site and the Sponsor, the subject's demographics and medical history

CONFIDENTIAL

This material is the property of Stryker Spine. Do not disclose or use except as authorized in writing by Stryker.

Page 20

will be recorded, preoperative functional evaluation will be completed; neurological status (reflex, sensory, motor; and subject's current pain medications will be documented; SF-12 (Q of L), VAS (back and leg), and ODI(function) will be collected; and AP/Lateral, Flexion/Extension and long standing lateral radiographs and an MRI/CT (to confirm diagnosis) will be taken.

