## **7.2 Peri-operative Visit**

During the peri-operative visit, the patient will undergo lumbar interbody fusion via the transforaminal approach with the AccuLIF Expandable Interbody Fusion Cage with supplemental fixation in the form of pedicle screws. Surgical details will be collected including: estimated blood loss (EBL), operative times including skin-to-skin and anesthesia time, implant and screw sizes, and any intraoperative complications will be collected at time of surgery. The length of hospital stay will be recorded upon discharge. Any adverse events occurring during surgery through discharge will be collected and reported.

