## **7.3 6 Week Visit**

During the 6 week visit (42 days after surgery  $\pm$  2 weeks, study days 28 – 56), SF-12, VAS (back and leg), ODI and patient satisfaction will be collected; neurological status (reflex, sensory, motor); subject's current pain medication, work status, and smoking status will be assessed. AP/Lateral radiographs will be taken.

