## 12.3 Expected Complications

A number of complications and adverse events may be anticipated during the course of the study. Many of these are a consequence of general surgical procedures. The more common serious possible risks and/or complications associated with general surgery are:

- Superficial or deep-set infection
- Pneumonia
- Clots (emboli) in the blood vessels or lungs
- Brusing or blood loss (hemorrhage)
- Reactions to the drugs or anesthetic agents used during and after surgery
- Scar tissue and/or heterotopic bone formation
- Inflammatory phenomena
- Nerve damage, numbness, weakness, sensory / motor loss
- Systemic infection, including urinary tract infection
- Change in mental status
- Phlebitis (painful and swollen veins)
- Post-surgical muscle or tissue pain and swelling at the incision
- Possible need for blood products
- Hyperthermia or hypothermia
- Pneumonia
- Decrease in bone density due to stress shielding
- Failure of the tissue to heal properly, wound infection, or wound dehiscence
- Reactions to transfused blood
- Injury to the spine during intubation
- In rare situations, blindness, cardiac arrhythmia, hypotension, heart attack, paralysis, stroke, or death.

Additional anticipated adverse events associated with the subject's surgery are included in the treating institution's standard consent form for surgery.

CONFIDENTIAL

This material is the property of Stryker Spine. Do not disclose or use except as authorized in writing by Stryker.  
Page 33

Since the AccuLIF Expandable Interbody Fusion Cage is implanted using a posterior /transforaminal approach some of its potential complications are specific to the method of entry (2, 3). The following risks are associated with the posterior / transforaminal surgical approach:

- Injury to nerves;
- Injury to blood vessels (arteries and veins) leading to bruising (hematoma) and swelling;
- Neurological and spinal dura mater lesions from surgical trauma;
- Neurological problems secondary to blood vessel injury such as cerebral ischemia, stroke, or gastrointestinal and/or genital side effects;
- Shortness of breath or breathing discomfort following removal of breathing tube;
- Injury to the lumbar plexus;
- Injury to the dura;
- Temporary or permanent loss of bowel or bladder function;
- Potential complication of pain from the incision in the hip to harvest bone; should it be taken;
- Pseudoarthrosis and failure to form visible bridging trabecular bone;
- Hemorrhage (blood loss);

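### The neurologic complication endpoint rests on pre/post examinations, with none specified between surgery and the 6-week visit and no link to adverse events, so early transient deficits are left out of its rate

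*Combined protocol and SAP*

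**What the plan says.** Section 2.2 states the secondary objective as "To assess the occurrence of neurologic complications by comparing pre-operative and postoperative neurologic evaluation". Section 9.1.4 turns this into "The occurrence of neurologic complications, defined as abnormal changes from the pre-operative to post-operative neurologic evaluations", under the introduction "The secondary parameters of the study, evaluated at each study visit, are as follows".

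The examinations behind that comparison are set out visit by visit in section 7. The baseline is in section 7.1 ("neurological status (reflex, sensory, motor; and" pain medication). The first post-operative examination is in section 7.3: "During the 6 week visit (42 days after surgery", plus or minus two weeks. The same examination recurs at 3, 6, 12 and 24 months (7.4 to 7.7). Section 7.2, the peri-operative visit, reads "Surgical details will be collected including: estimated blood loss (EBL), operative times including skin-to-skin and anesthesia time" and goes on to implant and screw sizes, intraoperative complications, hospital stay and adverse events up to discharge. It names no neurologic examination. The Evaluation Schedule likewise starts the post-operative functional evaluation at 6 weeks.

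Adverse events are handled separately. Those tied to the device, the operation or the lumbar spine, and all serious ones, are reportable from consent to study completion (8.1.1, 8.1.2), including between visits (8.4). They are summarised descriptively (9.2.2).

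**The concern.** The endpoint is named for the occurrence of complications but is built from a difference between examinations, the first of which comes at least four weeks after surgery. Harm to nerves from inserting a cage would be expected to show soon after the operation. Section 6.1 says the implant's small starting height is designed to "help to reduce the potential for neural injury during insertion of the implant", so this is the secondary endpoint closest to that design aim. Section 12.3 recognises that such harm may pass, for example "Temporary or permanent loss of bowel or bladder function".

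Two things are at stake. First, a figure reported as the occurrence of neurologic complications would in fact be the proportion with a deficit present at 6 weeks or later. Section 16 plans a first multi-center publication at 6 weeks, when only that one post-operative examination exists. Second, section 8.2 notes that adverse events may also be called complications. The study could therefore publish two different counts of neurologic complications, one from examinations and one from adverse events, with no rule that relates them.

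**Working it through.** **Step 1: the window.** Section 7.3 gives day 42 plus or minus 14 days: 42 − 14 = 28 and 42 + 14 = 56. This reproduces the stated study days 28 to 56. For a subject seen within the window, the time from surgery to the first specified neurologic examination is therefore 28 to 56 days.

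**Step 2: follow one subject through the rules.** Suppose a new motor or sensory deficit appears on the day after surgery and has gone by week 3.

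- Section 7.2: no neurologic examination is listed. The deficit is recordable as an adverse event before discharge.
- Sections 8.1.2 and 8.4: it remains reportable as an adverse event.
- Section 7.3: the examination matches baseline, so there is no abnormal change.
- Section 9.1.4, neurologic item: no event.
- Section 9.1.4, additional complications item: this is for complications other than the neurologic ones listed just before it; its examples are infection and nonunion.
- Section 9.2.2: counted in the descriptive safety summary, if reported.

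So the subject appears in the safety tables but not in the endpoint.

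**Step 3: direction and form of the bias.** Let p be the proportion of subjects with a new deficit after surgery, and f the share of these that resolve before the first examination. If the endpoint sees only unresolved deficits:

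- endpoint rate = p × (1 − f)
- absolute shortfall = p × f
- relative shortfall = f, whatever p is

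Since f cannot be negative, the omission cannot raise the rate.

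**Step 4: illustration.** The documents give neither p nor f. Both ranges below are assumptions, applied to the planned 100 subjects with all examined at 6 weeks. Entries are expected subjects counted, 100 × p × (1 − f).

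| Assumed p | Expected with a deficit | f = 25% | f = 50% | f = 75% |
|---|---|---|---|---|
| 2% | 2 | 1.5 | 1.0 | 0.5 |
| 5% | 5 | 3.75 | 2.5 | 1.25 |
| 10% | 10 | 7.5 | 5.0 | 2.5 |
| 15% | 15 | 11.25 | 7.5 | 3.75 |

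At p = 5% and f = 50%, the chance that the endpoint shows no case at all is (1 − 0.025)^100 = 8%. The table shows how the rule behaves; it does not estimate what this trial will see.

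**The case against.** The best case for the plan is that nothing is lost. Intraoperative complications and adverse events through discharge are collected (7.2), the investigator must ask about events at every contact and examine where appropriate (8.1.2), and nerve damage and sensory or motor loss are listed as anticipated (12.3). A standard pre/post examination is a legitimate, reproducible measure, and spontaneous reports belong in the safety summary; merging the two mixes methods of ascertainment. Section 9.1.4 also does not confine itself to scheduled examinations. Because its list includes operating time, blood loss and hospital stay, the study visits it refers to must include the peri-operative one.

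Much of this stands, and it rules out several stronger readings that a reader might infer:

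- *That early deficits go uncounted in the study.* They are subject to mandatory adverse event reporting and descriptive summary. They are missing from this endpoint, not from the trial.
- *That subjects are unobserved until day 28 to 56.* Adverse event collection is continuous. What is lacking is a specified neurologic examination.
- *That the plan admits only scheduled examinations.* It does not bar an in-hospital or unscheduled one. It requires none, however, and does not say that its result would count, so sites could differ.
- *That the device claim or a literature comparison depends on this rate.* Reduced neural injury is a design statement, not a study hypothesis, and section 9.1.6 does not name neurologic complications among the outcomes to be compared.

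What does not stand is the inference that adverse event capture repairs the endpoint. No section connects the two. The concern about mixed ascertainment is fair, and separate reporting of the components answers it.

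**Conclusion.** The point holds for the endpoint as written. It has no specified examination between surgery and the 6-week visit and no stated link to adverse events or intraoperative complications, so deficits that resolve in that interval are left out of its rate. The resulting bias, relative to the occurrence of neurologic complications, can only be downward.

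Its size is unknown. The relative shortfall equals the share of new deficits that resolve before the first examination, and the documents give nothing from which to estimate that share. The conclusion assumes a literal reading of 9.1.4 and no in-hospital examination counted by local choice; where sites do count one, the undercount shrinks but the rate is no longer defined uniformly. This is a secondary endpoint without a success criterion. The sample size rests on segmental lordosis (9.4.2) and is unaffected.

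**What to change.** In section 9.1.4, define a subject as having a neurologic complication if either of these holds:

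1. a neurologic adverse event or intraoperative neurologic complication with onset from surgery onward, whether or not it has resolved; or
2. a worsening from the pre-operative neurologic examination at any post-operative evaluation.

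Count each subject once. Report the examination-based and adverse-event-based components separately, and within the total separate transient from persistent deficits. Align section 2.2 with the new definition, and carry the rule into the formal statistical analysis plan that section 9.1.6 foresees.

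The cost is wording only: both sources are already collected, and no visit or procedure is added. The reported rate may be somewhat higher, and the combined figure mixes two kinds of ascertainment, which is why the components should be shown side by side.

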#### 9.1.5 Secondary Objective Analysis

Where changes from baseline can be calculated for numerical data, statistical analyses will be performed. Analyses will follow the two-sided approach taken for the primary analyses. Data that is ordinal in nature, such as the changes in clinical outcomes, may be analyzed using Wilcoxon signed rank tests, comparing baseline measures to follow-up measures. All analyses will be two-sided and evaluated at an alpha level of 0.05.

#### 9.1.6 Exploratory Objective Parameters

The exploratory parameters of the study, evaluated at each study visit, are as follows:

- The percentage of subjects that achieve  $> 3^\circ$  increase in lordosis and have no negative changes in regional lordosis and global sagittal balance
- Changes in disc height, lordosis, and sagittal balance as categorized by disc morphology. Disc morphologies are defined as:
  - **Tall and lordotic** Average Disc Height  $\geq 11$  mm **AND** Disc Angle  $> 12^\circ$ .

CONFIDENTIAL

This material is the property of Stryker Spine. Do not disclose or use except as authorized in writing by Stryker.  
Page 26

- **Moderate** Average Disc Height  $\geq 7$  mm to  $\leq 10$  mm **AND** Disc Angle  $\geq 5^\circ$  to  $\leq 12^\circ$ .
- **Flat and compressed:** Average Disc Height 0 mm to  $\leq 6$  mm **AND** Disc Angle  $0^\circ$  to  $< 5^\circ$ .

  

- The differences in AccuLIF data compared to published literature of comparable TLIF outcomes. The published literature sources will be identified in a formal statistical analysis plan.

### 9.1.7 Exploratory Objective Analysis

Exploratory analyses will be performed using the same methodology as the secondary analyses.

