#### 9.1.3 Primary Objective Analysis

CONFIDENTIAL

This material is the property of Stryker Spine. Do not disclose or use except as authorized in writing by Stryker.  
Page 25

For the primary endpoint of an increase of 3 degrees or more of segmental lordosis, a one-sided analysis (alpha=0.05) will be used to assess significance. A one-sample t-test will be employed. Although the primary analysis will be at 12 months, similar analyses will be performed at each visit. Both the change from baseline and the results at each visit will be summarized.

For all other radiographic parameters, the change from baseline will be analyzed at each visit using two-sided, one-sample t-tests (alpha=0.05) comparing the change from baseline to 0.

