## **12.5 Potential Benefits to Subject**

There is no guarantee that subjects will personally benefit from inclusion in this study. Subjects may undergo more thorough screening and follow-up than non-study patients and may benefit from this increased surveillance. This study seeks to provide clinicians information about this system/device by comparing this treatment/device to published results for other treatments/devices. Information gathered in this study may benefit others undergoing this procedure in the future.

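### Section 9.1.7 gives all exploratory objectives within-cohort tests, which cannot compare disc-morphology groups and carry no sampling error for published results

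*Combined protocol and SAP*

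**What the plan says.** Section 9.1.7 is a single sentence: "Exploratory analyses will be performed using the same methodology as the secondary analyses". It makes no exception for any objective.

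The secondary methods are in 9.1.5. For numerical data where a change from baseline exists, "Analyses will follow the two-sided approach taken for the primary analyses". The two-sided approach in 9.1.3 consists of "two-sided, one-sample t-tests (alpha=0.05) comparing the change from baseline to 0". Ordinal data "may be analyzed using Wilcoxon signed rank tests, comparing baseline measures to follow-up measures". Then: "All analyses will be two-sided and evaluated at an alpha level of 0.05".

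Sections 2.3 and 9.1.6 list three exploratory items. The first is the percentage of subjects meeting a composite lordosis and balance criterion. The second is change in disc height, lordosis and sagittal balance by disc morphology, which 2.3 words as a comparison. The third is "The differences in AccuLIF data compared to published literature of comparable TLIF outcomes". Section 9.1.6 leaves the choice of literature sources to a later formal SAP and says nothing there about method. Section 6.2 states that there is no control cohort. Section 12.5 says the study aims to inform clinicians by "comparing this treatment/device to published results for other treatments/devices".

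**The concern.** Both methods in 9.1.5 ask whether one cohort changed from its own baseline. The second and third exploratory items ask something else.

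For morphology, a test against 0 within each group does not estimate the difference between groups. If one group reaches p<0.05 and another does not, that is not evidence that they differ, because group size and spread alone can produce the pattern.

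For the literature, the result from a published series is itself an estimate with a standard error. Neither method in 9.1.5 has a place for it. The obvious way to adapt a one-sample test is to put the published mean in place of 0, and that would treat the published mean as known exactly.

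The literature is the study's only external comparator, the Synopsis names TLIF with a static cage as reference therapy, and section 16 plans multi-center papers at 6 weeks, 1 year and 2 years. What is at stake is how far readers can trust a claimed difference between AccuLIF and other cages, or between disc types.

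**Working it through.** **The plan's own figure.** The protocol states no error rate for the literature comparison. Its only computed figure is the sample size in 9.4.2: true change 5 degrees, threshold 3 degrees, SD 6 degrees, one-sided alpha 0.05, power 90%. For a one-sample t-test with difference 5 − 3 = 2, the noncentral t distribution gives n = 79 with power 90.2%, an exact match. With 20% dropout, 79/0.80 = 98.75, so 99, consistent with 100 enrolled. About 100 × 0.80 = 80 evaluable subjects is therefore a fair n for what follows.

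**Type I error if a published mean is the null value.** Inputs:
- n = 80 AccuLIF subjects (from 9.4.2).
- Two-sided nominal alpha 0.05 (from 9.1.5).
- m patients in one published series: assumed, not in the protocol.
- Literature SD equal to trial SD: assumed.

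The one-sample test divides the difference by SD/√n. With no true difference, the variance of that difference is SD²(1/n + 1/m), so the statistic has variance 1 + n/m rather than 1. The actual error is

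2 × [1 − Φ(1.96 / √(1 + n/m))].

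| m | √(1 + 80/m) | 1.96 / root | Formula | Simulated t (400,000 draws) |
|---|---|---|---|---|
| 30 | 1.915 | 1.024 | 0.306 | 0.3005 |
| 50 | 1.612 | 1.216 | 0.224 | 0.2189 |
| 100 | 1.342 | 1.461 | 0.144 | 0.1403 |
| 200 | 1.183 | 1.656 | 0.098 | 0.0960 |
| 500 | 1.077 | 1.820 | 0.069 | 0.0681 |
| 1,000 | 1.039 | 1.886 | 0.059 | 0.0588 |

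Because n/m is positive for every finite m, the error always exceeds 5%. The size depends on the assumptions.

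**Sensitivity, n = 79.** The term under the root becomes 1 + r²n/m + nτ²/SD², where r is literature SD over trial SD and τ is the between-study SD.
- r = 0.5: 12.8% at m = 30, 6.2% at m = 200.
- r = 1.5: 45.6% at m = 30, 15.4% at m = 200.
- r = 1, τ = 1 degree, SD 6 degrees: 41.7% at m = 30, 30.1% at m = 200.

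**Morphology.** No arithmetic is needed. A one-sample or signed rank test within each group yields no estimate, interval or test of the difference between groups.

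**The case against.** The strongest reply is that the plan never describes a test against a published value. The inherited methods compare change with 0 or follow-up with baseline, and neither admits a literature figure. The Synopsis and 2.3 speak of comparing summary AccuLIF data with the literature, the Synopsis limits exploratory analysis to where it is appropriate, and 9.1.5 calls for tests only where a change from baseline can be calculated. A side-by-side description with no test fits all of this. A later SAP could still set the method once the sources are known. The item is exploratory and does not touch the primary test or the sample size.

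Much of this stands. A reader might infer that the plan already treats published means as error-free and so has a false-positive rate of 10% to 31%. The documents do not support that: no section makes a published mean the null value, and no literature n, SD or number of series is given. Nor does the text show that chance differences will be reported as real.

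The reply does not remove the gap. Section 9.1.7 covers every exploratory objective without exception, and what 9.1.6 expressly leaves to the SAP is the sources. If the comparison is meant to be descriptive, the plan should say so. If it is to be tested, no usable method is stated. The morphology item could also be read as summaries within categories, but 2.3 sets out to compare changes, and the stated methods cannot do that.

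**Conclusion.** The concern holds in this form: the methods that 9.1.7 assigns do not answer two of the three exploratory objectives. For morphology this rests on the text alone. For the literature comparison, the firm defect is that no method carrying the uncertainty of the published estimate is specified.

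The inflation figures are conditional. They apply only if a one-sample test is run with a published mean as the null value, and they assume one series per comparison, 80 AccuLIF subjects, equal SDs and no between-study variation. On those terms the error is about 10% to 31% for 200 down to 30 patients and about 6% to 7% for 500 to 1,000. The direction is certain under that use; the size cannot be fixed from the documents. The primary analysis and its conclusion are unaffected.

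**What to change.** Replace 9.1.7 with methods matched to each objective.

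- **Literature.** Report the difference with a 95% confidence interval that includes the published standard error: Welch-type from the published mean, SD and n for a single series, or against a random-effects pooled estimate when several are used. Label it exploratory and unadjusted for case mix. Series without an SD are described only.
- **Morphology.** Estimate between-group differences in change with 95% confidence intervals, for example by one-way ANOVA or a linear model with morphology group. Do not adjust for the disc height or angle that defines the groups. Those bands (read here as pre-operative values) do not overlap, so an adjusted contrast would rest on extrapolation. State that regression to the mean may contribute, since the groups are formed on values that also enter the change score.

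The cost is SAP wording and modest analysis work, with no new data. Intervals against the literature become wider and fewer differences will be nominally significant. With SD 6 degrees and n = 80, treating the published mean as exact gives a half-width of 1.96 × 6/√80 = 1.31 degrees. Including its error gives 1.96 × 6 × √(1/80 + 1/30) = 2.52 degrees for a series of 30, and 1.96 × 6 × √(1/80 + 1/200) = 1.56 degrees for a series of 200.
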